10. HUMAN SUBJECTS

Inclusion criteria: Adult patients of at least 18 years of age, (1) having a total of 1-6 rib fractures at least 3 cm distal to the costo-transverse joint sustained within the previous 3 days (bilateral fractures are acceptable, but the total of the two sides combined must not exceed 6 fractures); (2) regional anesthetic requested by the admitting service; and, (3) accepting of a cryoneurolysis procedure.

Exclusion criteria: (1) chronic opioid use (daily use within the 2 weeks prior to surgery and duration of use > 4 weeks; of note, any testing for opioid use will not occur as part of the study, but as standard of care); (2) pregnancy; (3) incarceration; (4) inability to communicate with the investigators; (5) morbid obesity (body mass index > 40 kg/m²); (6) possessing any contraindication specific to cryoneurolysis such as a localized infection at the treatment site, cryoglobulinemia, cold urticaria and Reynaud's Syndrome; (7) any patient unable to correctly perform incentive spirometry as this is the primary outcome measure; (8) any patient with any degree of decreased mental capacity as determined by the surgical service; (9) any reason an investigator believes study participation would not be in the best interest of the potential subject; (10) flail chest; (11) chest tube; (12) fracture of the 1st rib on either side; or (13) any moderate or severe pain (NRS>3) unrelated to the rib fracture(s), as best determined by the patient and investigator.

11. RECRUITMENT AND PROCEDURES PREPARATORY TO RESEARCH

Study inclusion will be proposed to eligible patients at one of the UCSD Medical Center hospitals (listed in #3 above)—by an investigator part of the clinical treatment team involved in the patient's clinical care (HIPAA requirements will be adhered to). There is no minimum number of hours or days from the time of fracture until the time of study participation and no requirement for overnight admission. If a patient desires study participation, written, informed consent will be obtained using an IRB-approved informed consent form.

Selection for inclusion will not be based on sex, race, or socioeconomic status. For women of childbearing age with the possibility of pregnancy, a sample of urine is always collected for a

pregnancy test prior to an invasive procedure—regardless of study participation. Pregnant patients will be excluded from study participation.

12. INFORMED CONSENT

When a prospective subject desires, they will be provided information on the study purpose and protocol, as well as have any questions answered. Candidates who meet inclusion and exclusion criteria and desire study enrollment will be scheduled for treatment, usually the same day or the following day depending on staff/equipment availability, anti-coagulation status, and other factors. Written informed consent will be attained prior to any measurements or procedures. This will occur in private patient care rooms, so that subjects may feel comfortable asking questions.

Subjects will be provided ample privacy and time for decision making. Surrogate consent will not be accepted; therefore, if human subjects cannot provide consent on their own, they will not be offered study enrollment. Consent by an individual's Legally Authorized Representative is unacceptable for study enrollment. Of note, minors (age < 18 years) will not be offered enrollment. Therefore, assent will not be accepted during the informed consent process.

13. ALTERNATIVES TO STUDY PARTICIPATION

Potential study subjects may simply decline enrollment. They will still receive our standard-of-care analgesics.

14. POTENTIAL RISKS

1. Infection. There is the potential risk of infection since subjects will have a probe inserted through the skin. Since there will be nothing left going through the skin or in the subject after the probe is withdrawn, the risk of infection is very small and there has never been a report of permanent injury due to infection following cryoneurolysis.
2. Bleeding. The probe does not have an open tip and is not particularly sharp, so there is a very low risk of having any type of bleeding as a result of treatment. However, if it was to happen, we would hold pressure until the bleeding stopped.
3. The skin where the nerve is frozen could lose or gain color if the nerve is particularly close to the surface. However, this has never been reported for deeper nerves and using the probe that will be used for this study.
4. Since a nerve will be frozen, there is the chance of nerve injury. However, in multiple decades of using percutaneous cryoneurolysis on peripheral nerves, only a single case of "neuritis" (nerve irritation) has been reported in medical journals, and this resolved after a few months.
5. There is the risk of loss of confidentiality. The following procedures will be done to maintain confidentiality: written, paper forms will be kept in a locked medical. Computerized records containing personal health information will be stored on password-protected and encrypted computers.
6. The intercostal nerves run on the under surface of the ribs. Inserting a cryoneurolysis probe close enough to freeze these nerves therefore has a risk of injuring the lining of the lung resulting in pneumothorax. The risk of pneumothorax during such a procedure with ultrasound guidance is estimated from the literature as 1 in 2,000. However, the anesthesiologists performing these procedures have advanced training and years of experience that should further reduce this risk.
7. Pain. Cryoneurolysis has been demonstrated to provide pain relief for various chronic pain indications; but, it has not been rigorously investigated for acute pain states such as rib fractures. Therefore, subjects randomized to receive cryoneurolysis of the intercostal nerve(s) might

experience more pain during the first 6-8 hours after treatment than subjects receiving a local anesthetic-based intercostal nerve block; but, they also might experience less pain for the remainder of 2 months during the period of fracture healing.

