7. BACKGROUND AND SIGNIFICANCE

[figure not shown]
Rib fractures represent a significant source of morbidity in trauma patients, with approximately 10% of trauma patients presenting with rib fractures.¹ Pain from rib fractures is associated with decreased ability to cough and inspire deeply, predisposing patients to atelectasis and pulmonary complications. Neuraxial blocks, both thoracic epidurals and paravertebral blocks, have been associated not only with decreased pain, but also decreased pulmonary complications and overall mortality in patients with rib fractures.² Furthermore, intercostal nerve blocks with local anesthetic have been shown to improve pain scores, peak expiratory flow rates, and arterial oxygen saturation on room air.³ However, intercostal nerve blocks are not without risk and incidence of pneumothorax has been reported as 1.4% for each individual intercostal nerve that is blocked.⁴ Although it is possible that the use of in-plane ultrasound guidance may decrease the risk of pneumothorax, this has not been evaluated. Additionally, intercostal blocks with bupivacaine have been reported to resolve in as little as six hours,⁵ likely due to the high vascularity and consequent uptake of local anesthetic from the intercostal space.

An alternative analgesic technique is cryoneurolysis, consisting of the application of exceptionally low temperatures to *reversibly* ablate peripheral nerves, resulting in temporary pain relief termed “*cryoanalgesia*”.⁶ The intense cold temperature at the probe tip produces Wallerian degeneration—a reversible breakdown of the nerve axon—subsequently inhibiting transmission of afferent and efferent signals. Because the nerve endoneurium, perineurium, and epineurium remain

intact, the axon regenerates along the exoskeleton at a rate of approximately 1-2 mm/day. While cryoneurolysis of peripheral nerves through surgical incisions has been commonly used to treat pain since 1961, the development of cryo probes that may be inserted percutaneously promise a revolution in the use of this modality.

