9. RESEARCH DESIGN AND METHODS

The cryoneurolysis procedure will be compared with our current UCSD standard practice.

Study Overview

Day 0

Baseline pain levels and spirometry

Subjects randomized and cryoneurolysis/sham procedure administered
Post-block pain levels and spirometry repeated

Days 1, 2, 7	Pain levels, opioid consumption, sleep disturbances due to pain, and incentive spirometry values collected [day of discharge recorded]
Months 0.5, 1, 1.5 , 2 3, 6, and 12	Pain levels, opioid consumption, sleep disturbances due to pain, and pain interference collected [if subject has spirometer available]

Subjects will be individuals who present to one of the UCSD hospitals with rib fracture(s) and significant pain. The University of Florida will be following the same protocol and the subjects from both institutions will be combined for the analysis. Those who consent to participate in this study will have standard ultrasound-guided intercostal nerve blocks administered with ropivacaine 0.5% (with epinephrine), 3 mL/level of each fracture rib as well as one level above and one level below.

Treatment group assignment (randomization). Subjects will be allocated to one of two possible treatments stratified by treatment center and unilateral vs. bilateral fractures:

1. **active cryoneurolysis (*sham local anesthetic intercostal blocks*)**
2. **sham cryoneurolysis (*active local anesthetic intercostal blocks*)**

Computer-generated randomization lists will be used to create sealed, opaque randomization envelopes with the treatment group assignment enclosed in each envelope labeled with the randomization number.

The specific intercostal nerves targeted will depend on the injury site. The treatment sites will be cleansed with chlorhexidine gluconate and isopropyl alcohol. Using the optimal ultrasound transducer for the specific anatomic location and subject anatomy (linear vs curvilinear array), the target nerves will be identified in a transverse cross-sectional (short axis) view. The intercostal nerve of each fractured rib as well as the level above and below will be treated with the protocol below:

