Intercostal nerve block procedure: The target nerve will be visualized with ultrasound. Local anesthetic (1% lidocaine) will be used to infiltrate the skin and underlying muscle at each entry point. A 20 g Tuohy needle will be introduced through the skin wheel and along the anesthetized muscle tract. For subjects randomized to active cryo, 3 mL of normal saline will be injected into the muscle superficial to the nerve; and for subjects randomized to sham cryo, 3 mL of ropivacaine 0.5% (with epinephrine) will be injected perineurally to provide the intercostal nerve block.

Cryoneurolysis procedure: Cryoneurolysis probes are available for a console neurolysis device (PainBlocker, Epimed, Farmers Branch, Texas) that either (1) pass nitrous oxide to the tip inducing freezing temperatures; or, (2) vent the nitrous oxide at the base of the probe so that no gas reaches the probe tip, resulting in no temperature change. The latter is a sham procedure since without the temperature change, no ice ball forms and therefore the target nerve is not affected. An angiocatheter/introducer will be inserted beneath the ultrasound transducer and directed until the probe tip is immediately adjacent to the target nerve. The angiocatheter needle will be removed, leaving the angiocatheter through which the appropriate Epimed probe will be inserted until it is adjacent to the target nerve. The cryoneurolysis device will be triggered using 2 cycles of 2-minute gas activation (active or sham) separated by 1-minute defrost periods. For active probes, the nitrous oxide will be deployed to the tip where a drop in temperature to -70°C will result in cryoneurolysis. For the sham probes, the nitrous oxide will be vented prior to reaching the probe shaft, resulting in a lack of perineural temperature change.

The process will be repeated with the same treatment probe for any additional nerves (e.g., all nerves will receive either active cryoneurolysis or sham/placebo, and not a mix of the two possible treatments).

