17. POTENTIAL BENEFITS

For subjects randomized to receive a sham cryo treatment: There will be no difference between being in this study and deciding against participation. Therefore, there is no potential for direct benefits from this sham cryo "treatment".

For subjects randomized to receive active cryoneurolysis: It is our hope that patients have a decrease in their acute and chronic rib fracture pain (which might permit a decreased opioid consumption and opioid-related nausea/vomiting) and improved pulmonary mechanics measured by incentive spirometry.

Possible benefits to others: Future patients may benefit if it is determined that cryoneurolysis decreases pain and improves pulmonary function in patients with rib fractures. In addition, with the opioid epidemic, any decrease in opioid requirements would be a welcome development.

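### Does the uncited 1 in 2,000 pneumothorax risk contradict the background's 1.4% per nerve in a way that requires a change to the plan?

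*Combined protocol and SAP*

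**What the plan says.** Section 7 (Background and Significance) describes intercostal nerve blocks with local anesthetic and says that "incidence of pneumothorax has been reported as 1.4% for each individual intercostal nerve that is blocked", with a reference. The next sentence adds: "Although it is possible that the use of in-plane ultrasound guidance may decrease the risk of pneumothorax, this has not been evaluated".

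Section 14 (Potential Risks), item 6, turns to inserting a cryoneurolysis probe near the intercostal nerve: "The risk of pneumothorax during such a procedure with ultrasound guidance is estimated from the literature as 1 in 2,000". It carries no reference number. It then says that the operators' training and experience should lower the risk further.

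The number of nerves treated varies between subjects. Section 9 (Research Design and Methods) says "The intercostal nerve of each fractured rib as well as the level above and below will be treated". Section 10 (Human Subjects) admits one to six fractures: "bilateral fractures are acceptable, but the total of the two sides combined must not exceed 6 fractures".

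Two further places bear on the point. Section 9 describes a cryoneurolysis introducer in both arms: "An angiocatheter/introducer will be inserted beneath the ultrasound transducer and directed until the probe tip is immediately adjacent to the target nerve". The block needle differs by arm: in the active cryoneurolysis arm "3 mL of normal saline will be injected into the muscle superficial to the nerve", while the sham cryoneurolysis arm has ropivacaine injected at the nerve. Section 17 (Potential Benefits) says of the sham arm: "There will be no difference between being in this study and deciding against participation".

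**The concern.** Taken together, Sections 7 and 14 seem to say that the effect of ultrasound is unknown and also that the literature supplies a rate with ultrasound. The favourable figure is the only one in the risk section. It has no citation, and the only title about pneumothorax in the bibliography is the source of the 1.4%. Because several nerves are treated in each subject, it matters whether 1 in 2,000 refers to a nerve or a patient, and the text does not settle this.

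Two side issues add to the impression. Section 17 can be read as saying that sham subjects undergo nothing extra, although they receive an additional introducer placement at each level. And the statistical section plans no count of pneumothorax by arm, although a pneumothorax could lower inspired volume, the primary endpoint.

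If the conflict were substantive, the stated balance of risk and benefit would rest on a figure that the protocol's own background does not support, and a safety event relevant to the primary endpoint would go unreported by arm.

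**Working it through.** **Can the stated figure be reproduced?** No. The 1 in 2,000 comes without a numerator, denominator or source, so only its consistency with Section 7 can be checked.

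**Inputs.**
- p = 0.014 per nerve (Section 7).
- q = 1/2,000 = 0.0005, unit unclear (Section 14, item 6).
- k, the nerves treated per subject (Sections 9 and 10). One fracture with a level above and below gives k = 3. Six adjacent fractures on one side give 6 + 2 = 8. Three adjacent fractures on each side give 2 × (3 + 2) = 10.
- Maximum enrollment of 30 (Section 9).

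**If 1 in 2,000 is per nerve.** The ratio is p/q = 0.014/0.0005 = 28. Ultrasound would have to remove 1 − 0.0005/0.014 = 96.4% of the cited risk for the two figures to agree.

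**Per-patient risk**, assuming independent nerves, is 1 − (1 − risk per nerve)^k:

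| k | at 1.4% per nerve | at 1/2,000 per nerve |
|---|---|---|
| 3 | 1 − 0.986³ = 4.1% | 1 − 0.9995³ = 0.15% |
| 8 | 1 − 0.986⁸ = 10.7% | 1 − 0.9995⁸ = 0.40% |
| 10 | 1 − 0.986¹⁰ = 13.2% | 1 − 0.9995¹⁰ = 0.50% |

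**If 1 in 2,000 is per patient.** The risk stays at 0.05%. The 1.4% figure then implies 0.04141/0.0005 = 83 times that for three nerves and 0.10666/0.0005 = 213 times for eight.

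**Expected subjects with pneumothorax among 30.** At 1.4% per nerve: 30 × 0.04141 = 1.2 (k = 3) to 30 × 0.10666 = 3.2 (k = 8). At 1/2,000 per nerve: 0.045 to 0.12. At 1/2,000 per patient: 0.015.

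The table carries a local-anesthetic block figure over to cryoneurolysis with no ultrasound benefit. It measures how far apart the two statements are and does not estimate the risk in this trial. Nor is all of that risk added by the trial, since Section 10 requires that a regional anesthetic has already been requested.

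**Do the sentences exclude each other?** Section 7 addresses a comparison: whether in-plane ultrasound lowers the risk of intercostal nerve blocks. Section 14 gives an absolute rate for ultrasound-guided insertion of a cryoneurolysis probe. A rate can be observed or extrapolated without anyone having compared techniques. The statements sit awkwardly together but are not logically incompatible.

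**Does either figure feed the design or analysis?** The sample size in Section 9 uses a 250 mL difference and an SD of 148 mL. The primary test is Welch's test on inspired volume the day after treatment. Neither figure appears in these, and neither sets a procedure or contact schedule.

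**Would a count by arm inform?** With no events in ten subjects, the exact two-sided 95% upper limit is 1 − 0.025^(1/10) = 30.8%.

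**The case for a change.** The strongest case for a change runs as follows. Section 7 calls cryoneurolysis essentially the same procedure as an ultrasound-guided nerve block, so the difference in technique is a thin defence of a 28-fold gap. Section 18 judges the risks minimal, and the only pneumothorax figure behind that judgement is unsourced. Subjects in the sham arm receive real intercostal blocks, yet Section 14 gives no pneumothorax figure for those blocks. The remedy would cost a few words, one form entry and one table row.

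Part of this stands. Item 6 would be clearer with a source and a stated denominator, and the reader is left to guess how it relates to the 1.4%. But no item in Section 14 carries a reference, so the missing citation reflects how the whole section is written. The sentence does name a denominator, the procedure, although it is ambiguous. The consent pages are not among the documents, so nothing can be concluded about what participants are told.

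The side issues are weaker. The sentence after the Section 17 statement concludes that the sham treatment offers no direct benefit, so in context the statement is about benefit, although it is loosely worded given the extra introducer. As to a count by arm, adverse events already go to the IRB (Sections 15 and 18), and nothing prevents the analyst from listing them by group. A formal count would be hard to read. Section 10 excludes a chest tube but not an existing pneumothorax, so injury-related and procedural cases would mix. Section 9 collects follow-up by phone, so later contacts would find only diagnosed or reported cases.

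**Conclusion.** The quotations and the arithmetic hold. The protocol gives a referenced 1.4% per nerve in one section and an uncited 1 in 2,000 in another, 28-fold apart on a per-nerve reading and further apart if the second figure is per patient. What does not hold is the step from there to a defect in the plan. The figures describe different procedures, one statement is comparative and the other absolute, and the documents cannot show which figure is right or that either is wrong.

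This is a documentation slip in the risk text. Aligning the two sections would improve disclosure but would leave the treatment procedures, sample size, primary endpoint, analysis and conclusions as they are. A count by arm in about ten subjects per group would be too imprecise to support an inference (0/10 is compatible with up to 30.8%), and adverse events are already reported. The per-patient percentages assume independent nerves, no ultrasound benefit and that the block figure transfers to cryoneurolysis. The conclusion that no change follows depends on none of these assumptions.

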15. RISK MANAGEMENT PROCEDURES AND ADEQUACY OF RESOURCES

During the treatment, subjects will be continuously monitored with pulse oximetry, noninvasive blood pressure cuffs, and EKG (standard for nerve blocks). If one is not already present, subjects will receive an IV so that emergency medications could be given, if needed. As described above, probes will be placed under sterile conditions as is standard-of-care for any percutaneous cryoneurolysis.

Following treatment, the subjects will be contacted daily for the first 2 days, and then on days 7 and 14, as well as months 1, 1.5, 2, 3, 6 and 12. Subjects will have a physicians' pager and cellular phone numbers available to respond 24 hours/day and 7 days/week for at least the first week following treatment.

The risks to confidentiality are the release of names/ telephone numbers/ demographic data (e.g. weight, age, height), which will be minimized by the use of password-protected computers and case report forms that will be stored in locked offices.

Subjects will be given clear instructions to call an investigator with any questions or concerns regarding their study participation. If a patient experiences an injury that is directly caused by this study, medical care will be provided at the medical center. No other compensation is offered. Any adverse events will be reported to the IRB using the standard adverse events reporting and upon continuing review (depending on severity, as defined by the IRB).

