The combination of newly-designed narrow-gauge probes (upper right) and ultrasound now make percutaneous cryoanalgesia as simple as placing a peripheral nerve block: the probe tip is inserted adjacent to the target nerve under ultrasound guidance, and a series of 2-minute freezing cycles are administered followed by probe withdrawal. ***The procedure is essentially the same as placing an ultrasound-guided peripheral nerve block; however, instead of injecting local anesthetic, a gas circulates through the probe, inducing cold at the tip and freezing the target nerve.***

Nothing remains within the patient and there is no external equipment to prepare or manage. Importantly, cryoneurolysis and the probes are already approved by the United States Food and Drug Administration for the treatment of acute and chronic pain, so no additional regulatory approval is required for the proposed clinical trial.

Theoretical benefits of cryoneurolysis include an ultra-long duration of pain control without opioid involvement, no catheter management/removal (reducing infection risk), the lack of an infusion pump and anesthetic reservoir to carry, an extraordinarily-low risk of infection (approaching zero), and no risk of local anesthetic toxicity, catheter dislodgement or leakage. With a single 8-minute percutaneous cryoneurolysis procedure consisting of several freeze/defrost cycles, a truncation of sensory nerve conduction is induced for 6-8 weeks, with the complete restoration of nerve structure and function following remyelination. Cryoneurolysis offers the possibility of potent, side effect-free analgesia outlasting the surgical pain, and obviating the need for postoperative opioids.

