For subjects at the University of Florida, their anthropomorphic, baseline, procedure, and post-procedure data will be recorded on the same case report form as at the University California San Diego and faxed to the investigators at UC San Diego following the procedure. These faxed documents will remain in electronic form (eFax) on the Principal Investigator's password-protected, encrypted, UCSD-owned MacBook computer. Investigators at UC San Diego will do all of the follow-up data collection by phone for subjects at both treatment centers.

Outcome measurements (end points). Anesthesia providers will perform all measures and assessments, which will include:

1. **Pain:** measured on the 11-point NRS of pain intensity
2. **Opioid consumption**
3. **Pain interference:** measured using the Brief Pain Inventory (which includes the pain scores of #1 above)
4. **Sleep disturbances (#):** due to pain
5. **Pulmonary Mechanics:** measured by the inspired volume on a handheld incentive spirometer based on the American Association of Respiratory Care (AARC) clinical practice guideline.⁷ The best of three measurements will be recorded as the maximum inspired volume.

Statistical Analysis: The primary endpoint is the maximum inspired volume measured by incentive spirometry the day following treatment. There is no accepted minimal clinically-relevant change in incentive spirometry volume. However, the median (IQR) of inspired volume for patients with rib fracture(s) is 1250 (750-1750) mL,⁸ and, ISV<1000 mL is associated with an increased risk of acute respiratory failure.⁸ We will therefore use the difference between 1250 and 1000 (250 mL) as the minimal clinically-relevant difference. However, there is high variability in the reported increase in inspired volume with various regional analgesic interventions such as continuous intercostal nerve blocks⁹ and serratus plane blocks,¹⁰ and we will therefore increase our enrollment to account for an unpredicted increase in variability or non-normal data distribution.

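### The protocol specifies no adverse-event question at any of its ten follow-up contacts and no safety outcome, so five of the seven named risks depend on chance observation or spontaneous report after the procedure

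*Combined protocol and SAP*

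**What the plan says.** Section 15 places the follow-up contacts under risk management: contact is made "daily for the first 2 days, and then on days 7 and 14, as well as months 1, 1.5, 2, 3, 6 and 12". The Study Overview in section 9 gives the same schedule and says what is gathered. On days 1, 2 and 7 this is: "Pain levels, opioid consumption, sleep disturbances due to pain, and incentive spirometry values collected", plus the day of discharge. From month 0.5 to month 12 it is pain, opioid use, sleep disturbance and pain interference, with spirometry if the subject has a device.

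The outcome list in section 9 opens with "Anesthesia providers will perform all measures and assessments, which will include" and has five entries: pain, opioids, pain interference, sleep and pulmonary mechanics. The statistical analysis text mentions no adverse events. Section 9 also says that follow-up data for both centers are collected by phone. Section 11 states "no requirement for overnight admission".

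On harms, section 14 lists seven risks. Section 15 provides monitoring during the procedure, a physician line ("Subjects will have a physicians' pager and cellular phone numbers available to respond 24 hours/day and 7 days/week for at least the first week following" the procedure), an instruction without an end date to call an investigator with concerns, and reporting of adverse events to the IRB. Section 18 repeats the last two.

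**The concern.** Reporting an event to the IRB presupposes that someone has found it. The protocol names the risks and schedules ten conversations with each subject, yet it gives no question, checklist, time window or grading by which those conversations would bring the risks to light.

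Three things are at stake. First, a harm that appears after the subject has gone home may not be found unless the subject raises it, and data not asked for at the time cannot be recovered later. Second, unprompted reports need not arise equally in the two arms, and both arms have a needle and a probe placed at every treated level. Third, section 14 says of nerve injury that "only a single case of 'neuritis' (nerve irritation) has been reported in medical journals, and this resolved after a few months". A similar event here would enter the record only as more pain, which the collected items cannot separate from fracture pain. Chronic pain at 6 and 12 months is the subject of hypotheses 2c and 2d, so the cause of late pain is something readers will want to know.

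**Working it through.** **Contacts.** Section 9: days 1, 2, 7 (3) plus months 0.5, 1, 1.5, 2, 3, 6, 12 (7) = 10. Section 15: days 1, 2, 7, 14 (4) plus months 1, 1.5, 2, 3, 6, 12 (6) = 10. The lists agree, with day 14 as month 0.5. Contacts that list an adverse-event item: 0 of 10. Outcomes that concern safety: 0 of 5.

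**Section 14 risks against what is collected.**

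| Risk | Could be noticed during the procedure | Asked at scheduled contacts |
|---|---|---|
| 1. Infection | No | No |
| 2. Bleeding | Yes, by the operator | No |
| 3. Skin colour change | Not relied on | No |
| 4. Nerve injury | Not relied on | No; at most a higher pain or interference score |
| 5. Confidentiality | Not applicable | Not a matter for a call |
| 6. Pneumothorax | Possibly, by ultrasound or pulse oximetry | No; spirometry is an indirect signal |
| 7. Pain | Measured again after the block | Yes, at all ten |

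Seven risks, less pain and confidentiality, leaves 7 − 2 = 5 with no scheduled question after the procedure.

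**What solicited data could show.** Section 9 plans 10 evaluable subjects per group and at most 30 enrolled, or 15 per group if split equally. With zero events in n subjects, the exact two-sided 95% upper limit is 1 − 0.025^(1/n):
- n = 10: 1 − 0.025^(1/10) = 0.308, about 31%.
- n = 15: 1 − 0.025^(1/15) = 0.218, about 22%.

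Full elicitation would therefore give counts and descriptions, not a precise rate.

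**Illustration: pneumothorax.** Section 7 cites 1.4% per intercostal nerve blocked and says that any reduction from ultrasound has not been evaluated. Section 14 gives 1 in 2,000 for the procedure under ultrasound. With 1 to 6 fractured ribs plus one level above and one below, and assuming the ribs are adjacent and on one side, 3 to 8 nerves are treated. Expected events in 20 subjects:
- At 1.4% per nerve: 20 × 3 × 0.014 = 0.84 to 20 × 8 × 0.014 = 2.24.
- At 1 in 2,000 per subject: 20 × 0.0005 = 0.01.

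These figures cover early and late events together, and some would be seen without a question. They show only that the documents' own figures leave the expected number uncertain by a factor of 84 to 224. The conclusion does not depend on them.

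**The case against.** The strongest reply is that the protocol is not the whole record. Section 9 refers to a case report form for procedure and post-procedure data, and that form is not in the documents. The outcome list is not stated to be exhaustive, and section 15 lists the calls under risk management. A reader might infer that subjects would never be asked about harms. The documents do not show that; they show only that the protocol text does not require it. This part of the reply stands.

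Four other stronger readings are tempting and also fail:

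- *Every named harm is captured only if the subject volunteers it.* Pain is asked about at every contact. The operator or the monitoring may reveal bleeding or pneumothorax during the procedure. Spirometry on days 0, 1, 2 and 7 may flag a respiratory problem, and subjects who stay in hospital are under clinical care.
- *The physician line is too short for the duration of the block.* One week is a stated minimum, the instruction to call has no end date, and seven of the ten contacts fall after day 7. Section 7 says "a truncation of sensory nerve conduction is induced for 6-8 weeks", but that is the intended effect, not a stated period of hazard. The few months in section 14 are the time one case took to resolve. Nothing here contradicts anything else.
- *Unrecorded harms bias the endpoints.* A harm caused by treatment that lowers inspired volume or raises pain is part of that treatment's effect. What is lost is the explanation, not the validity of the comparison.
- *Asking would let the trial confirm the low complication rate on which section 18 relies.* At this size it would not, as the 31% limit shows.

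None of this supplies a means of finding the five remaining harms after the procedure.

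**Conclusion.** The point holds as a gap in specification that should be closed. The protocol text sets out no adverse-event elicitation at any of ten contacts, no safety outcome and no harms table. After the procedure, infection, late bleeding, skin colour change, nerve injury and late pneumothorax rest on incidental observation or spontaneous report, in a trial followed by phone with no overnight stay required. A neuritis would not be distinguishable from fracture pain in the data listed.

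This rests on the protocol text alone. If the case report form already has a solicited harm section used at each call in both arms, what remains is to write it into the protocol and plan its tabulation. The gap does not invalidate the primary comparison of inspired volume on the day after treatment.

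**What to change.** Add a short fixed set of harm questions to the ten calls already scheduled:
- new breathlessness or a diagnosed pneumothorax;
- bleeding or haematoma;
- infection;
- skin colour change;
- new burning pain, or numbness beyond the expected block;
- unplanned care.

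Use the same wording in both arms. State who asks and over what period, and record onset and resolution. Say in advance how expected sensory block is told apart from a reportable nerve injury. Add a safety paragraph to the statistical analysis that tabulates counts by arm with exact confidence intervals. It should state that about 10 per arm supports detection and description but cannot establish a low rate.

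Answers about numbness may hint at the allocation. If the caller is meant to be masked, it is sensible to take the pain and spirometry items first at each call.

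The cost is a short amendment, one form page, about two minutes per call and more minor events to record. No extra visits or procedures are needed.
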